ANC = absolute neutrophil count; AST = aspartate aminotransferase; ALT = alanine aminotransferase; CBC = complete blood count; CT = computerized tomography; DNA = deoxyribonucleic acid; ECHO = echocardiogram; eCRF = electronic case report form; G-CSF = granulocyte-colony stimulating factor; HBV = hepatitis B virus; HCV = hepatitis C virus; INR = international normalized ratio; ILD = interstitial lung disease;

LVEF = left ventricular ejection fraction; MRI = magnetic resonance imaging; NCI-CTCAE = National Cancer Institute Common Terminology Criteria for Adverse Events; PK = pharmacokinetics; QTcF = QT interval corrected for heart rate using Fridericia's formula; RNA = ribonucleic acid; SpO₂ = peripheral capillary oxygen saturation; TBL = total bilirubin; TPN = total parenteral nutrition; ULN = upper limit of normal.

During study treatment, subjects who develop systolic and/or diastolic hypertension that is deemed by the Investigator to be clinically significant should receive treatment with anti-hypertensive therapy according to the Investigator's judgment and local institutional guidelines.

In addition, Investigators may consider dose reductions or discontinuations of the study drug according to the subject's condition and after discussion with Daiichi Sankyo's Medical Monitor or designee.

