5.4. Dose Modifications (Dose Delay, Reduction, and/or Discontinuation)

All dose modifications (delay, reduction and/or discontinuation) should be based on the worst grade toxicity of the event preceding the dose modification. Dose modifications are applicable only to TEAEs that are assessed as related to use of U3-1402 by the Investigator(s). For non-drug related TEAEs, follow standard clinical practice. Appropriate clinical experts should be consulted as deemed necessary. All dose modifications must be recorded on the AE and drug administration electronic case report form (eCRF) pages.

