5.4.1.3. Dose Modifications

[Table 5.2](#) provides schedule modifications for specific toxicities.

Table 5.2: Dose Modification Criteria

| | Worst Toxicity NCI-CTCAE Version 5.0 Grade (unless otherwise specified) | Schedule Modification for U3-1402 |
|---|--|---|
| General disorders and administration site conditions | | |
| Infusion related reaction (eg, same reduced rate as previous infusion) | Grade 1 Mild transient reaction; infusion interruption not indicated; intervention not indicated | If infusion related reaction (such as fever and chills, with and without nausea/vomiting, pain, headache, dizziness, dyspnea, hypotension) is observed during infusion, the rate must be reduced by 50% and subjects must be closely monitored. If no other reactions appear, the subsequent infusion rate can be resumed at the initial planned rate. |
| | Grade 2 Therapy or infusion interruption indicated but responds promptly to symptomatic treatment (eg, antihistamines, nonsteroidal anti-inflammatory drugs [NSAIDs], narcotics, intravenous [IV] injection fluids); prophylactic medications indicated for ≤ 24 hours | U3-1402 infusion must be interrupted. Symptomatic treatment (eg, antihistamines, NSAIDs, narcotics, IV fluids) administered as needed. If the event resolves or improves to Grade 1, infusion can be re-started at a 50% reduced infusion rate. Upon restart, if Grade 2 symptoms recur, no further U3-1402 must be administered at that visit. The amount of U3-1402 infused must be recorded in the eCRF. Subsequent infusions must be conducted at the 50% reduced infusion rate (ie, same reduced rate as previous infusion). |

| | Worst Toxicity NCI-CTCAE Version 5.0 Grade (unless otherwise specified) | Schedule Modification for U3-1402 |
|---|---|--|
| | Grade 3 Prolonged (eg, not rapidly responsive to symptomatic medication and/or brief interruption of infusion); recurrence of symptoms following initial improvement; hospitalization indicated for clinical sequelae Grade 4 Life-threatening consequences; urgent intervention indicated | Administration of U3-1402 must be discontinued immediately and permanently. Urgent intervention indicated. Antihistamines, steroids, epinephrine, bronchodilators, vasopressors, IV fluid therapy, oxygen inhalation etc., must be administered as clinically indicated. |

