13.7. National Cancer Institute Common Terminology Criteria for Adverse Events, Version 5.0

1. Toxicity Grade should reflect the most severe degree occurring during the evaluated period, not an average.
2. When 2 different criteria Grades might be applicable for rating a particular toxicity, or similar toxicities, the more severe Grade should be used.
3. Any toxicity resulting in death is defined as Grade 5.
4. The evaluator must attempt to discriminate between disease/treatment and related signs/symptoms.
5. For links to the NCI-CTCAE v5.0, please refer to
http://ctep.cancer.gov/protocolDevelopment/electronic_applications/ctc.htm#ctc_40

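### Table 5.2 gives two incompatible actions for an infusion reaction that improves, is restarted at half rate and recurs with Grade 2 symptoms

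*Combined protocol and SAP*

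**What the plan says.** The relevant text is in the protocol, Section 5.4.1.3, Table 5.2, under infusion related reaction.

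- **Grade 2, restart:** the infusion is interrupted and symptoms are treated. Then "If the event resolves or improves to Grade 1, infusion can be re-started at a 50% reduced infusion rate".
- **Grade 2, recurrence:** "Upon restart, if Grade 2 symptoms recur, no further U3-1402 must be administered at that visit".
- **Grade 2, later infusions:** "Subsequent infusions must be conducted at the 50% reduced infusion rate".
- **Grade 3, definition:** after a prolonged reaction, the list continues with "recurrence of symptoms following initial improvement; hospitalization indicated for clinical sequelae".
- **Grades 3 and 4, action:** "Administration of U3-1402 must be discontinued immediately and permanently".

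Two general rules bear on the choice of row. Section 5.4 says "All dose modifications (delay, reduction and/or discontinuation) should be based on the worst grade toxicity of the event preceding the dose modification". Section 13.7 says "When 2 different criteria Grades might be applicable for rating a particular toxicity, or similar toxicities, the more severe Grade should be used". Section 5.2.4, on administration, refers back to Table 5.2 for dosing after an infusion reaction and adds no rule of its own.

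**The concern.** The Grade 2 row anticipates a reaction that settles, is restarted and comes back, and it stops drug for that visit. The Grade 3 row treats symptoms that come back after first improving as Grade 3 and stops drug for good. Both are worded as mandatory, and a site cannot follow both for the same subject.

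The first consequence is for subjects. One reading allows further exposure after a printed permanent-stop criterion has been met. The other ends treatment for someone whom the Grade 2 row appears to keep on it. Section 1.2.2 names infusion-related reaction as a potential risk and notes possible allergic or anaphylactic reactions, so the case is foreseeable. With approximately 40 planned sites (Section 3.1), different handling at different sites is also foreseeable.

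The second consequence is for the safety tables. Section 11.5.2.1 summarizes treatment-emergent events by worst CTCAE grade and by action taken, including treatment discontinuation. The same event could be counted as Grade 2 with treatment continuing, or as Grade 3 with discontinuation, depending on the row the site used.

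**Working it through.** No arithmetic applies. The check traces one event through the printed rows and then looks for a rule elsewhere that settles it.

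**Tracing the event**

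1. A Grade 2 reaction occurs and the infusion is interrupted.
2. The event resolves or improves to Grade 1. This is the row's own condition for a restart, and it is an initial improvement.
3. The infusion restarts at the 50% rate.
4. Grade 2 symptoms recur.

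| | Grade 2 row | Grade 3 row |
|---|---|---|
| Does the event fit? | Yes: Grade 2 symptoms recurring on restart | Yes: symptoms recurring after improvement (steps 2 and 4) |
| Action at this visit | Stop | Stop |
| Action afterwards | Stop limited to this visit; the row goes on to give the rate for later infusions | Permanent discontinuation |

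The rows agree about the current visit and disagree about everything after it.

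**How far the overlap extends.** Step 3 is allowed only after step 2. Any recurrence on restart under the Grade 2 row has therefore followed an improvement. So every case that the Grade 2 recurrence sentence covers also meets the literal Grade 3 criterion.

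The reverse does not hold. A recurrence that is prolonged, needs hospitalization or is life-threatening lies outside the Grade 2 sentence, falls only under the Grade 3/4 rows and has one action.

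**Looking for a rule that settles it**

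- Section 5.4 ties the modification to the worst grade of the event. Section 13.7 assigns the more severe grade when two might apply. Together they point to the Grade 3 row. Since all cases under the Grade 2 recurrence sentence also meet the Grade 3 criterion, that sentence is then left with nothing to govern.
- The closing text of Section 5.4.1.3 lets investigators consider reductions or discontinuations after discussion with the medical monitor. It does not say how this event is graded.
- Section 5.7 lets a subject who meets a discontinuation criterion stay on treatment with sponsor approval if there is evidence of benefit. That is a case-by-case exception. It is unlikely to help after a reaction at the first infusion, because the first scheduled on-study tumor assessment is at week 6 (Section 3.1.2).

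The general grading rules and the specific table instruction therefore contradict each other, and no passage reconciles them.

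**The case against.** **The protocol already has a tie-break.** This is the strongest point, and part of it stands. A reader might infer that the plan leaves two equally valid instructions with nothing to choose between them. The documents do not support that: Sections 5.4 and 13.7 together direct a site to the higher grade. What they do not do is remove the conflict. Applying them empties a sentence that the table states explicitly, and a site that reads only Table 5.2 would not see the tie-break.

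**The rows can be read as compatible.** The Grade 2 sentence itself calls the returning symptoms Grade 2 and concerns re-exposure at a reduced rate. The Grade 3 phrase stands next to prolonged reactions and hospitalization, so it might mean symptoms that return despite treatment and without further drug. The column heading also allows for grades specified otherwise. This reading is possible, but the printed criterion draws no such distinction and nothing else in the documents supplies one. It also leads to the opposite action from the tie-break, so it confirms that the text needs clarifying.

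**Later dosing after a recurrence is inferred.** A reader might say that the Grade 2 row expressly orders re-dosing of such a subject. It does not quite do so. The sentence on subsequent infusions closes the whole row and also fits a subject whose restart succeeded. Because the stop is limited to one visit and that sentence follows without restriction, later dosing is strongly implied, but it is not separately stated for the recurrence case. Even on the narrow reading, the Grade 2 row does not call for permanent discontinuation.

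**The effect may be small, and recording guidance may exist.** This is fair. Sections 1.1.5 and 1.2.2 give no infusion-reaction rate, and the reaction is listed as a potential risk, not an identified one. Section 9.5 refers to an eCRF Completion Guide that is not among the documents and may contain recording instructions. It would not change the actions printed in Table 5.2.

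**Conclusion.** The concern holds as an internal inconsistency and should be fixed. It rests on the printed wording of Table 5.2 and on the grading rules in Sections 5.4 and 13.7, and on no statistical assumption.

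Its extent is limited. A reader might infer that every infusion reaction that recurs after restart carries two opposite instructions. That is too broad, because only recurrences of Grade 2 symptoms do.

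The number of subjects affected is unknown, since the documents give no rate. As a conversion only, each 1% of the approximately 80 planned subjects is 80 × 0.01 = 0.8 subject. The case for a change rests on what the instructions decide, namely permanent discontinuation, and not on frequency.

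The ORR definition and analysis, the sample size and the interim criteria do not depend on this point. The effect on reporting is confined to the grade and action taken for these events. Nothing here takes a position on which clinical rule is right.

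**What to change.** Reconcile the Grade 2 recurrence sentence with the Grade 3 definition and action in Table 5.2, consistently with Sections 5.4 and 13.7, so that a recurrence of Grade 2 symptoms after restart has one grade and one action. State in the same row whether the sentence on subsequent infusions applies after such a recurrence or only after a successful restart. Carry the result into the eCRF grading instructions so that grade and action taken are recorded in the same way at all sites. Which rule applies is for the sponsor's safety team to decide.

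The cost is a wording change in one table at the next amendment, matching text in the eCRF instructions and a letter to sites. No procedures, visits or subjects are added.

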5.4.1. Dose Delay and Reductions

5.4.1.1. Dose Delay and Discontinuation

The dose can be delayed for up to 28 days from the planned date of administration (ie, 49 days from the last infusion date). If a subject is assessed as requiring a dose delay longer than 28 days, the subject should be discontinued from the study treatment.

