5.4.1.2. Dose Reductions

If dose reduction is required, U3-1402 dosing should be reduced by 1 dose level at a time ([Table 5.1](#)). Once the dose of U3-1402 has been reduced due to an AE, all subsequent cycles should be administered at that lower dose level unless further dose reduction is required.

Dose reductions for the fixed dose 5.6 mg/kg regimen are described in [Table 5.1](#).

Table 5.1: Dose Reductions for the Fixed Dose 5.6 mg/kg Regimen

| Starting Dose | Dose Level -1 | Dose Level -2 |
|---------------------------|---------------------------|---------------------------|
| 5.6 mg/kg IV infusion Q3W | 4.8 mg/kg IV infusion Q3W | 3.2 mg/kg IV infusion Q3W |

IV = intravenous; Q3W = every 3 weeks

Subjects will be withdrawn from the study treatment if further toxicity meeting the requirement for dose reduction occurs.

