| Fatigue/Asthenia/ Malaise | Grade 3 | Delay dose until resolved to \leq Grade 1 or baseline values, then: 
• If resolved to \leqGrade 1 or baseline values in \leq14 days, resume U3-1402;• If resolved to \leqGrade 1 or baseline values in $>$14 days, reduce U3-1402 by 1 dose level and resume. |
| Blood and lymphatic system disorders | | |
| Neutrophil count decreased | Grade 3 (500 to $<$ 1000/mm ³ ; $0.5 \times 10^9/L$) | Delay dose until resolved to \leq Grade 2, then resume U3-1402. |
| | Grade 4 ($<$ 500/mm ³ ; $<0.5 \times 10^9/L$) | Delay dose until resolved to \leq Grade 2, then reduce U3-1402 by 1 dose level and resume. |
| Febrile neutropenia (ANC $<$1000/mm³; $<1 \times 10^9/L$, fever $>$38.3°C or a sustained temperature of \geq38°C for more than 1 hour) | Grade 3 | Delay dose until resolved, then resume U3-1402. Consider reducing U3-1402 by 1 dose level. Consider administration of G-CSF as prophylaxis for all subsequent cycles and according to local guidelines. |
| Febrile neutropenia (ANC $<$1000/mm³; $<1 \times 10^9/L$, fever $>$38.3°C or a sustained temperature of \geq38°C for more than 1 hour) | Grade 4 | Delay dose until resolved, then reduce U3-1402 by 1 dose level and resume. Administer G-CSF as prophylaxis for all subsequent cycles and according to local guidelines. |

| | Worst Toxicity NCI-CTCAE Version 5.0 Grade (unless otherwise specified) | Schedule Modification for U3-1402 |
|------------------------------------|--|---|
| Lymphocyte count decreased | Grade 4 ($<0.2 \times 10^9/L$) | Delay dose until resolved to \leq Grade 2, then: 
 • If resolved in \leq14 days, resume U3-1402. • If resolved in $>$14 days, reduce U3-1402 by 1 dose level and resume. |
| Anemia | Grade 3 (Hemoglobin <8.0 g/dL) | Delay dose until resolved to \leq Grade 2 or baseline, then resume U3-1402. For recurrent anemia, delay dose until resolved to \leq Grade 2 or baseline, then reduce U3-1402 by 1 dose level and resume. Consider transfusion per institutional guidelines. |
| | Grade 4 Life-threatening consequences; urgent intervention indicated | Delay dose until resolved to \leq Grade 2 or baseline, then reduce U3-1402 by 1 dose level and resume. Consider transfusion per institutional guidelines. |

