| Platelet count decreased | Grade 3 (Platelets $<50 - 25 \times 10^9/L$) | Delay dose until resolved to \leq Grade 1, then: 
 • If resolved in \leq14 days, resume U3-1402; • If resolved in $>$14 days, U3-1402 may be resumed. Consider reducing U3-1402 by 1 dose level. Consider transfusion per institutional guidelines. |
| | Grade 4 (Platelets $<25 \times 10^9/L$) | Delay dose until resolved to \leq Grade 1, then reduce U3-1402 by 1 dose level and resume. Consider transfusion per institutional guidelines. |
| Cardiac disorders | | |
| Heart failure | Grade ≥ 2 (Symptoms with moderate activity or exertion) | Cardiologist consultation as necessary. Delay dose until resolved to \leq Grade 1, then reduce U3-1402 by 1 dose level and resume. |
| Ejection fraction decreased | Decrease in LVEF 10% to 20% (absolute value), but LVEF $>45\%$ | Continue U3-1402. |
| | LVEF 40% to $\leq 45\%$ and decrease is $<10\%$ (absolute value) from baseline | Continue U3-1402. Repeat LVEF assessment within 3 weeks. |
| | LVEF 40% to $\leq 45\%$ and decrease is 10% to 20% (absolute) from baseline | Delay U3-1402 dosing. Repeat LVEF assessment within 3 weeks. If LVEF has not recovered to within 10% (absolute value) from baseline, discontinue subject from study treatment. |

| | Worst Toxicity NCI-CTCAE Version 5.0 Grade (unless otherwise specified) | Schedule Modification for U3-1402 |
|--|---|--|
| | LVEF <40% or >20% (absolute) drop from baseline | Delay U3-1402 dosing. Repeat LVEF assessment within 3 weeks; if LVEF <40% or >20% (absolute) drop from baseline is confirmed, discontinue U3-1402. Cardiologist consultation as necessary. |
| Electrocardiogram QT corrected interval prolonged | Grade 3 (Average QTcF \geq 501 ms; >60 ms change from baseline) | Delay U3-1402 until resolved to \leq Grade 1 (QTcF \leq 480 ms). Determine if another medication the subject was taking may be responsible and can be adjusted or if there are any changes in serum electrolytes that can be corrected. If QTcF prolongation is attributed to U3-1402, then reduce U3-1402 by 1 dose level. Cardiologist consultation as necessary. |
| | Grade 4 (Torsade de pointes; polymorphic ventricular tachycardia; signs/symptoms of serious arrhythmia) | Discontinue subject from U3-1402. Cardiologist consultation as necessary |

| | Worst Toxicity NCI-CTCAE Version 5.0 Grade (unless otherwise specified) | Schedule Modification for U3-1402 |
|--|--|---|

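### Table 5.2 directs re-dosing after drug-related Grade 4 heart failure that recovers in time, unless a separate stop applies; a Grade 4 discontinuation line should be added

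*Combined protocol and SAP*

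**What the plan says.** The heart failure entry in Table 5.2, under Cardiac disorders, is one row for Grade 2 and above, described as "Symptoms with moderate activity or exertion". It calls for a cardiologist if necessary, a delay until the event has fallen to Grade 1 or lower, a reduction of one dose level, and resumption. It has no separate Grade 3 or Grade 4 line and no discontinuation branch.

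Four other rules bear on this row:

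- Section 5.4: dose modifications "should be based on the worst grade toxicity of the event preceding the dose modification", and they apply only to treatment-emergent events judged related to U3-1402.
- Section 5.4.1.1: a dose may be delayed up to 28 days from its planned date. "If a subject is assessed as requiring a dose delay longer than 28 days, the subject should be discontinued from the study treatment".
- Section 5.4.1.2: two reductions are available, to 4.8 and then 3.2 mg/kg. "Subjects will be withdrawn from the study treatment if further toxicity meeting the requirement for dose reduction occurs".
- The ejection fraction rows of Table 5.2 carry their own stops. At 40% to 45% with a fall of 10 to 20 points, the dose is delayed and LVEF repeated within 3 weeks: "If LVEF has not recovered to within 10% (absolute value) from baseline, discontinue subject from study treatment". For the larger falls, after the repeat: "if LVEF <40% or >20% (absolute) drop from baseline is confirmed, discontinue U3-1402".

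Section 9.4.3 defines Grade 4 as life-threatening. In the same cardiac block, the Grade 4 QTc line ("Torsade de pointes; polymorphic ventricular tachycardia; signs/symptoms of serious arrhythmia") discontinues the subject.

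**The concern.** An open-ended row combined with a worst-grade rule sends life-threatening heart failure down the same path as symptoms on moderate exertion. If the event is drug-related and recovers quickly enough, the row that names it tells the site to give the drug again. The other cardiac category graded by CTCAE, QTc prolongation, stops at Grade 4. The row's descriptor suggests it may have been drafted with milder disease in mind, though the protocol does not say so.

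What is at stake is the safety of an individual subject re-exposed after a life-threatening cardiac event. Section 1.2.2 lists cardiotoxicity among the nonclinical findings, so the cardiac rules should be explicit. No estimate, error rate or sample size is involved.

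**Working it through.** The plan states no figure to reproduce, so the check is to trace the rule and compare the row with the rest of the table.

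**Tracing the rule.**

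1. A subject has heart failure judged related to U3-1402, with worst Grade 4. Table 5.2 applies (Section 5.4, relatedness condition).
2. The action is set by the worst grade, which is 4 (Section 5.4).
3. The only heart failure row covers Grade 2 and above, so it includes Grade 4.
4. The row's action is to delay to Grade 1 or lower, reduce one level and resume.
5. If recovery comes within 28 days of the planned dose date, Section 5.4.1.1 does not force a stop.
6. If a lower dose level remains, Section 5.4.1.2 does not force a stop. From 5.6 mg/kg the subject resumes at 4.8 mg/kg (4.8/5.6 = 85.7% of the starting dose). From 4.8 mg/kg the subject resumes at 3.2 mg/kg (3.2/5.6 = 57.1%). A subject already at 3.2 mg/kg is withdrawn.
7. If no ejection fraction stop is met, those rows do not force a stop either. LVEF is scheduled only at screening and end of treatment, and otherwise as clinically indicated (Table 13.1), and the heart failure row does not itself require one.

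Nothing else in the documents makes discontinuation mandatory for Grade 4 heart failure as such.

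**Comparing Grade 4 actions across Table 5.2** (hand count; a Grade 4 line may be combined with Grade 3).

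| Group | Categories | Grade 4 action |
|---|---|---|
| Non-hematologic with a Grade 4 line | infusion reaction, QTc, pulmonary toxicity (ILD), ocular, creatinine, AST/ALT, bilirubin, vomiting, diarrhea/colitis, oral mucositis, other adverse events | 11 of 11 discontinue |
| Hematologic | neutrophils, febrile neutropenia, lymphocytes, anemia, platelets | 5 of 5 may resume |
| Heart failure | one row, Grade 2 and above | resumes one level lower |

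Grade 4 COVID-19 also ends treatment (Table 13.5). Of the three cardiac categories, QTc and ejection fraction each have a stop rule. Heart failure has none.

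**The case against.** The strongest reply is that the remaining gap is small and already guarded. The row calls for a cardiologist where necessary. Mandatory stops still operate through LVEF thresholds, the 28-day limit and the dose floor. The text after Table 5.2 lets the investigator consider discontinuation after talking to the medical monitor, and Section 5.7 lists adverse events and investigator discretion as reasons to stop. Section 4.2 excludes LVEF below 50%, recent NYHA Class 2–4 and recent infarction. A life-threatening event is serious and must be reported within 24 hours (Section 9.5), so the sponsor would know of it promptly. All of this stands and limits the size of the point. None of it is a Grade 4 stop: consultation and discretion are optional, and the mandatory stops depend on LVEF, time or dose level, not on grade.

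A second reply is that resuming after Grade 4 is a deliberate choice elsewhere. For febrile neutropenia the Grade 4 line reads "Delay dose until resolved, then reduce U3-1402 by 1 dose level and resume". This also stands: a reader might infer that Grade 4 is a universal stop in this protocol, and it is not. But the hematologic categories each have an explicit Grade 4 line, whereas heart failure reaches Grade 4 only because its range has no ceiling.

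A reader might also infer that sites could choose between conflicting rows. The documents give this little support. The catch-all row is headed as other adverse events, so by its wording it covers events without a row of their own. Nothing in the heart failure row suspends a stop triggered by LVEF.

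**Conclusion.** The point holds as a minor safety correction. As written, Table 5.2 directs re-dosing after drug-related Grade 4 heart failure that recovers to Grade 1 or lower within the permitted delay, when no LVEF stop is met, a dose level remains and the investigator does not choose to stop. That is out of line with all 11 non-hematologic categories that have a Grade 4 line.

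It would be too strong to say that every Grade 4 heart failure leads back to dosing, or that stopping rests on discretion alone; the mandatory stops above rule that out. Nor do the documents support an appreciable expected number of cases. They give no heart failure rate, and the lists of identified and potential human risks in Section 1.2.2 name no cardiac event. Section 1.1.5 reports Grade 3 or higher troponin increase in 3 of 36 NSCLC subjects (8.3%), but that is not heart failure and its cause is not stated. Few subjects are likely to be affected, and the efficacy analysis is unchanged.

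The conclusion rests on reading the row's grade range literally and on the worst-grade rule applying to it as to every other row.

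**What to change.** Limit the existing heart failure row to Grades 2–3 with its current action. Add a Grade 4 line with the same action as the Grade 4 QTc line: take the subject off U3-1402, with cardiology input as needed.

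Two further changes may look attractive but should not be made on this ground. A table-wide rule that the most conservative row governs could, if the catch-all row were read as overlapping named rows, turn the intended Grade 4 hematologic resumptions into stops. Cytopenias are among the commonest severe events on this drug: in Section 1.1.5, Grade 3 or higher neutrophil count decreased in 25.7% and platelet count decreased in 22.2% of breast cancer subjects, and platelet count decreased in 19.4% of NSCLC subjects. A mandatory LVEF condition for Grades 2–3 goes beyond the Grade 4 gap shown here.

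The cost is one row split in the next amendment and a rare additional discontinuation. The stop need not be absolute: Section 5.7 already allows a subject who meets a discontinuation criterion but is benefiting to continue with sponsor approval.
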